#### **14.6.2 ECG**

QT interval data will be presented using Fridericia's (QTcF) corrections.

ECG variables will be summarised by treatment and time point. Differences from baseline (Day 1 pre-dose) will be summarised by treatment and time point.

QTcF values > 450 msec, PR interval shortening < 110 msec, and PR interval prolongation > 220 msec, and increases of QTcF from baseline of > 30 msec and > 60 msec, will be listed by treatment and timepoint and summarised. A separate listing of ECG findings classified as abnormal by the investigator will also be provided.

### **14.6.3 Physical examination**

Abnormal physical and neurological examination findings will be listed.

### **14.6.4 Columbia-Suicide Severity Rating Scale (C-SSRS)**

Positive C-SSRS data will be listed.

## **15 Pharmacokinetic analyses**

The PK parameters to be derived are given in Appendix B: Pharmacokinetic analysis.

PK concentration data will be summarised using the PK analysis population.

Plasma concentrations and PK parameters will be listed and summarised, by treatment, using descriptive statistics. Individual and mean plasma concentration–time profiles will be presented graphically. All available data will be used to derive PK parameters in individual subjects.

For log–transformed parameters, the primary measure of central tendency will be the geometric mean; for other parameters, it will be the arithmetic mean or median.

For all variables, N (number of subjects receiving the treatment/formulation in the population), n (number of observations), arithmetic mean, median, minimum, maximum, standard deviation (SD), %CV, and the 95% CI for the arithmetic mean will be provided. For log-transformed variables, all of the above plus the geometric mean, which is the anti-logged arithmetic mean of log-transformed variables, its 95% CI and the SD of the logs will be provided.

The between-subject CV will be calculated using:

1. %CVb = 100 \* (SD/mean) with SD and mean of untransformed data
2. %CVb = 100 \*  $\sqrt{(\exp(SD)^2 - 1)}$  with SD of log-transformed data

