16.2.8 Pharmacokinetic data analyses

PK data will be summarised using the PK analysis population.

For log-transformed parameters, the primary measure of central tendency will be the geometric mean¹⁵; for untransformed parameters, it will be the arithmetic mean or median.

For all variables, N (number of subjects in receiving the treatment in the population), n (number of observations), arithmetic mean, median, minimum, maximum, SD, %CV, and the 95% CI of the arithmetic mean will be derived. For log-transformed variables, all of the above plus the geometric mean, its 95% CI, and the SD of the log-transformed variables, will be provided.

Plasma concentrations and PK parameters will be listed and summarised, by treatment, using descriptive statistics. Individual and mean plasma concentration–time profiles will be presented graphically. All available data will be used to derive PK parameters in individual subjects.

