**Template T\_PK3**

Table 14..2.xx Summary of derived ASN51 plasma pharmacokinetic parameters

Parameter	Treatment	Study Day	n	Mean	95% CI (Lower,Upper)	SD	%CVb	Median	Min	Max
AUC t (units)	Treatment 1 (N=xx)		xx	xxxx.xx	(xxxx.xx,xxxx.xx)	xx.xxx	xx.x	xxxx.xx	xxxx.x	xxxx.x
	Treatment 2 (N=xx)		xx	xxxx.xx	(xxxx.xx,xxxx.xx)	xx.xxx	xx.x	xxxx.xx	xxxx.x	xxxx.x
C max (units)	Treatment 1 (N=xx)		xx	xxxx.xx	(xxxx.xx,xxxx.xx)	xx.xxx	xx.x	xxxx.xx	xxxx.x	xxxx.x
	Treatment 2 (N=xx)		xx	xxxx.xx	(xxxx.xx,xxxx.xx)	xx.xxx	xx.x	xxxx.xx	xxxx.x	xxxx.x

Source: Listing 16.2.xx

Rac (AUC) = Rac (AUCtau) Day 14 / Rac(AUCtau) Day 1

Rac (Cmax) = Rac (Cmax) Day 14/Rac(Cmax) Day 1

Programming notes: *Continued with all dose levels, timepoints and parameters*

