**Template T\_PK4**

Table 14..2.xx Summary of log-transformed derived ASN51 plasma pharmacokinetic parameters {by group}

Parameter	Treatment	Study Day	n	Geom Mean	95% CI (Lower,Upper)	SD (logs)	%CVb
AUC last (units)	Treatment 1 (N=xx)	x	x	xxxx.xx	(xxxx.xx,xxxx.xx)	xx.xxx	xx.xx
	Treatment 2 (N=xx)	x	x	xxxx.xx	(xxxx.xx,xxxx.xx)	xx.xxx	xx.xx
C max (units)	Treatment 1 (N=xx)	x	x	xxxx.xx	(xxxx.xx,xxxx.xx)	xx.xxx	xx.xx
	Treatment 2 (N=xx)	x	x	xxxx.xx	(xxxx.xx,xxxx.xx)	xx.xxx	xx.xx

Source: Listing 16.2.xx

*Programming notes: Continued with all dose levels, timepoints and parameters*

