## 2 Parameter Definitions

### 2.1 Plasma Parameters

Text Symbol	Definition	Calculation	Typical Units	Log Transform	WNL	CDISC Controlled Terminology	TFL Symbol
Concentrations during and after multiple dosing							
C trough	Trough plasma concentration	Trough plasma concentration (measured concentration at the end of a dosing interval at steady state [taken directly before next administration, and at 1 dosing interval after the final dose]) obtained directly from the concentration-time data.	ng/mL	Y	-	CTROUGH	C trough
Concentrations and times (Day 1 and after final dose)							
C max	Maximum (peak) plasma concentration	Obtained directly from the concentration-time data.	ng/mL	Y	Cmax	CMAX	C max
C max /Dose	Dose-normalised C max	Calculated as C max /Dose administered	(ng/mL)/mg	Y	Cmax_D	CMAXD	C max /D
t max	Time to reach maximum (peak) plasma concentration	Obtained directly from the concentration-time data.	h	N	Tmax	TMAX	t max
Half-life (after final dose)							
λ z	Terminal rate constant	Estimated by linear regression of logarithmically transformed concentration versus time data.	1/h	Y	Lambda_z	LAMZ	λ z
t 1/2	Terminal half-life	Calculated from the terminal slope of the log concentration-time curve, as follows: $t_{1/2} = \frac{\log_e 2}{\lambda_z}$	h	Y	HL_Lambda_z	LAMZHL	t 1/2

Text Symbol	Definition	Calculation	Typical Units	Log Transform	WNL	CDISC Controlled Terminology	TFL Symbol
Areas under the curve (Day 1 and after final dose)							
AUC t	Area under the plasma concentration-time curve during a dosing interval (t)	Calculated using the trapezoidal method.	h*ng/mL	Y	User specified area	AUCTAU	AUC tau
Areas under the curve (after final dose)							
AUC last	Area under the plasma concentration-time curve from time zero to time of last measurable concentration	Calculated using the trapezoidal method.	h*ng/mL	Y	AUCLast	AUCLST	AUC last

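### SAP section 15 puts the square in the wrong place in the CV formula for log-transformed PK parameters; coded as printed, it inflates %CVb about 2.5 to 5 times for true CVs of about 9% to 50%

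*SAP*

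**What the plan says.** SAP section 15 introduces the formulas with "The between-subject CV will be calculated using" and lists two.

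- Formula 1 is 100 times SD over mean, "with SD and mean of untransformed data".
- Formula 2 is `100*sqrt(exp(SD)^2 - 1)`, "with SD of log-transformed data". The bracket closes after SD and the square follows it.

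The same section defines the log-scale location measure as the "geometric mean, which is the anti-logged arithmetic mean of log-transformed variables", to be reported with its 95% CI and the SD of the logs.

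Formula 2 feeds Table 14.2.1.3, template T_PK4, titled "Summary of log-transformed derived ASN51 plasma pharmacokinetic parameters". Its columns are n, geometric mean, 95% CI, SD (logs) and %CVb. The untransformed counterpart is template T_PK3, "Summary of derived ASN51 plasma pharmacokinetic parameters", to which formula 1 applies.

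The "Log Transform" column of SAP Appendix B, section 2.1, marks 11 parameters Y: Ctrough, Cmax, Cmax/Dose, λz, t½, AUCtau, AUClast, AUCinf, AUCinf/Dose, CLss/F and Vz/F.

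Protocol section 16.2.8 promises %CV, the geometric mean with its CI, "and the SD of the log-transformed variables, will be provided". It gives no CV formula for log-transformed data, and Appendix B gives none either.

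**The concern.** Squaring `exp(SD)` is not the same as exponentiating the squared SD. The first equals `exp(2*SD)`; the log-normal CV needs `exp(SD^2)`. Formula 2 is the only instruction for the %CVb column of T_PK4, so a programmer who follows the SAP literally will produce a wrong column for all 11 parameters.

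For these parameters the SAP makes the geometric mean the primary measure of central tendency, and this CV is one of the spread statistics printed beside it. A reader who took it at face value would believe that exposure varies far more between subjects than it does. T_PK3 and T_PK4 would also contradict each other for the same parameter and the same subjects.

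**Working it through.** **Inputs.** Both formulas come from SAP section 15. The group size of up to 6 comes from Protocol section 8.1.1. The documents give no CV or log-scale SD for ASN51, so there is no figure of the plan's own to reproduce, and the log-SD values below are assumptions. Natural logs are assumed; the SAP does not state the base for the PK parameters.

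**Correct form.** If ln X is normal with mean m and SD s:

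- mean of X = `exp(m + s^2/2)`
- variance of X = `(exp(s^2) - 1) * exp(2m + s^2)`
- CV = SD/mean = `sqrt(exp(s^2) - 1)`

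**Printed form.** `sqrt(exp(s)^2 - 1) = sqrt(exp(2s) - 1)`.

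**Behaviour.** For small s a CV should approach s, and the correct form does. The printed form approaches `sqrt(2s)`, which is much larger. The two agree only where s² = 2s, that is at s = 0 or s = 2. Above s = 2 the printed form is too small.

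**Worked example, s = 0.30.**

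- Correct: `100*sqrt(exp(0.09) - 1)` = 30.7%
- Printed: `100*sqrt(exp(0.60) - 1)` = 90.7%
- Ratio: 90.7 / 30.7 = 3.0

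**Range of assumed log-SD.**

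| SD (logs) | Correct %CVb | As printed | Ratio |
|---|---|---|---|
| 0.05 | 5.0 | 32.4 | 6.5 |
| 0.10 | 10.0 | 47.1 | 4.7 |
| 0.20 | 20.2 | 70.1 | 3.5 |
| 0.30 | 30.7 | 90.7 | 3.0 |
| 0.40 | 41.7 | 110.7 | 2.7 |
| 0.50 | 53.3 | 131.1 | 2.5 |
| 0.60 | 65.8 | 152.3 | 2.3 |
| 1.00 | 131.1 | 252.8 | 1.9 |

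The ratio is 5 at a log-SD of 0.087 (true CV 8.7%) and 2.5 at 0.477 (true CV 50.5%).

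**Check of the correct form by simulation.** With 4,000,000 log-normal draws, SD/mean is 9.0% at s = 0.09, 30.7% at s = 0.30 and 50.0% at s = 0.4724, in agreement with `sqrt(exp(s^2) - 1)`.

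**What the tables would show.** Medians over 200,000 simulated log-normal groups of 6:

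| True log-SD | Arithmetic %CVb (T_PK3) | Correct geometric %CVb | T_PK4 as printed |
|---|---|---|---|
| 0.20 | 18.5 | 18.8 | 67.2 |
| 0.30 | 27.6 | 28.5 | 86.6 |
| 0.50 | 45.0 | 49.3 | 124.2 |

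With the correct formula the two tables roughly agree at this group size. With the printed one they do not.

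**The case against.** The strongest objection is that the square may have moved when the PDF was converted to text. Other equations were visibly damaged: the extrapolation term for AUCinf in SAP Appendix B is garbled, although Protocol section 16.1.1 shows it properly. A superscript that slips across a bracket can leave an expression that still looks well formed, so its coherence does not prove that the signed SAP reads this way. That stands, and it is why confirming the original comes first. If the author meant the square to act on SD inside the exponential, the notation as it appears still codes to the wrong quantity.

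A second objection is that an experienced PK programmer would use the right formula regardless. That may be so; the documents do not show the program. But SAP section 3 requires deviations from the SAP to be documented in the CSR, so correct code would depart from the stated formula, while literal code would give a wrong table.

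Third, little depends on this column, and the error can be recovered. T_PK4 prints SD (logs) next to %CVb, individual parameter values are listed, and the clash with T_PK3 would be easy to notice. The trial tests no hypotheses, and the Group 2 decision rests on safety, tolerability and predicted individual Cmax and AUC24. All of this is true. It limits the harm to one descriptive column but does not make the formula right.

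**Conclusion.** The concern holds for the SAP text as supplied: formula 2 is not the log-normal CV, and nothing else in the protocol or SAP corrects it. Coded literally, it would overstate %CVb by about 5 times at a true CV near 9% and about 2.5 times at a true CV near 50%, across 11 parameters in Table 14.2.1.3.

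This rests on three assumptions: the signed SAP prints the exponent where the extracted text shows it, the program follows the SAP literally, and the log-SDs fall in the assumed range (natural logs).

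The consequence is limited. Geometric means and their CIs, SD (logs), the arithmetic %CVb in T_PK1 and T_PK3, the PBMC analyses and the Group 2 criteria do not use this formula. It should be corrected before the PK tables are finalised, but it threatens no primary conclusion.

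**What to change.** 1. Check the position of the superscript in the signed SAP.
2. If it matches the text reviewed here, rewrite formula 2 in SAP section 15 as `%CVb = 100*sqrt(exp(SD^2) - 1)`, where SD is the standard deviation of the natural-log-transformed data. Naming the log base removes a second possible ambiguity.
3. Check the T_PK4 program against a known value: SD (logs) of 0.300 must return 30.7%, not 90.7%.

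The cost is one moved exponent, a few words on the log base and one program check. No new data are needed. The SAP has already been reissued as version 1.1 for a formatting error and a removed table column, so a correction of this size has a precedent.

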### **15.1 Pharmacokinetic concentration data**

Plasma concentrations will be listed and summarised by treatment.

Using actual sample times, linear and semi-logarithmic concentration-time plots will be prepared by treatment and synoptic linear and semi-logarithmic plasma concentration-time plots of ASN51 will be prepared for each Day. In addition to the plots of concentrations on PK days, separate plots of trough concentrations for ASN51 will be prepared. The same linear and logarithmic scales will be used for each subject. The linear and semi logarithmic plots for a given treatment will be presented on the same page.

Nominal blood sampling times will be used to calculate the mean (SD) drug concentrations at each time point.

Mean(+/- SD), and spaghetti plasma concentration versus time plots will be presented for ASN51 per treatment (synoptic plot) (normal scale and log-linear scale).

## 15.2 Pharmacokinetic parameters

The pharmacokinetic parameters will be listed and summarised by treatment.

## 16 Pharmacodynamic analyses

Protein O-GlcNAcylation in PBMCs at each planned assessment, and change in protein O-GlcNAcylation in PBMCs from baseline (Day 1, pre-dose) at each planned post baseline assessment, will be summarised by actual treatment using the PD population.

Time invariance of target engagement will be investigated by comparing the PD and PK/PD relationship over time.

Food effect on the PBMC assay will be investigated by comparing Day 11 and 14 PBMC data descriptively.

In addition to the descriptive statistics of the PBMC data (ie N, mean, median, SD, min, max, CV%), time-matched change from baseline PBMC parameters (Day 1 vs Day 14, and Day 11 vs Day 14) will be assessed using an Analyses of variance (ANOVA) approach. ANOVA will be performed on the natural log(ln)-transformed PBMC parameters. Each ANOVA will include calculation of least square means (LSM), the difference between LSM of the two conditions, and the standard error and 90% confidence interval (CI) associated with this difference. The LSM, difference in LSMs, and associated 90% CI will be back transformed to present geometric LSM, the ratio of geometric means, and associated 90% CI. The 90% CI of geometric mean ratio will be calculated to check whether it lies within the interval 0.70 to 1.43.

Furthermore, PBMC data and plasma concentration data of Day 1 and Day 14 will be investigated by a regression analysis, where the slopes and intercepts will be compared statistically for each treatment. The change from baseline of PMBC data will be analysed using analysis of covariance (ANCOVA). Time point, PK concentration and PK concentration by time point interaction will be fitted as fixed effects. PK concentration will be treated as a continuous covariate and time point will be fitted as a categorical covariate. The estimates, standard errors, associated 95% CI and P-values will be reported.

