6.6 Rationale for choice of doses

6.7 Assessment and management of risk

Risk associated with ASN51 (all subjects)

Other safety considerations (all subjects)

[figure not shown]
Any other safety risk to study participants is mitigated by the following considerations.

- Subjects will be monitored frequently throughout the study for safety and tolerability, including vital signs, 12-lead safety ECG, physical and neurological examination, laboratory safety tests, and C-SSRS. The safety monitoring practices employed by this protocol are adequate to protect the subjects' safety and should detect all expected TEAEs.
- HMR maintains its own resuscitation team (SS329) to deal with medical emergencies, including anaphylaxis and cardiac arrest. The team will be on duty continuously, until at least 24 h after each dose.
- Any risks are adequately mitigated by safety assessments, and by the medical cover provided by the investigator site, and by appropriate investigational medicinal product (IMP) manufacture, according to Good Manufacturing Practice (GMP).
- Subjects will stay on the ward from the day before first study drug administration until 6 days (ie 3 half-lives) after the last study drug administration.

There will be no direct health benefit for study participants from receipt of study medication. An indirect health benefit to the healthy subjects enrolled in this trial is the free medical examination received at screening and during the study.

Overall, the risk benefit balance of the present study is considered to be acceptable.

Risk of testicular toxicity (all subjects)

Risk associated with the imaging techniques (PET subjects only)

In this study, each subject will be exposed to radiation from PET and computed tomography (CT) scans (for attenuation correction). To mitigate this risk, the study will exclude subjects who have had previous exposure to ionising radiation such that, their exposure would be $> 10\text{mSv}$ for the previous year (see exclusion criterion 35).

The maximal radiation exposure for each subject over the whole study is presented in Table 2.

Table 2: Expected maximal radioactive exposure of each subject

Assessment	Number of scans	Activity from PET tracer (MBq)	Effective dose per scan (mSv)	Total exposure (mSv)
PET emission scan	3	100	2.05	6.15
Low-dose CT scan	3	–	0.28	0.84
Total				6.99

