19. Plasma samples for the PBMC assay will be collected as follows.

PBMC-only subjects

- before and at 4, 8, and 12 h after dosing on Day 1
- before dosing on Day 2
- before and at 4 h after dosing on Day 11
- before and at 4 h, 8 h, and 12 h after dosing on Day 14
- at 24 h (Day 15), 72 h (Day 17), and 144 h (Day 20) after the last dose of ASN51

PET subjects

- before and at 4, and 8 h after dosing on Day 1
- before dosing on Day 2
- 4 h after dosing on Day 11
- before and at 4 h, and 8 h after dosing on Day 14
- at 24 h (Day 15), 72 h (Day 17), and 144 h (Day 20) after the last dose of ASN51

20. Plasma samples for PK assay of ASN51 will be collected at as follows.

PBMC-only subjects

- before and at 0.25, 0.5, 1, 1.5, 2, 3, 4, 6, 8, 12, and 16 h after dosing on Day 1
- before dosing on Days 2, 4, and 7
- before and at 8 h after dosing on Day 11
- before and at 0.25, 0.5, 1, 2, 4, 6, and 12 h after dosing on Day 14
- at 24 h (Day 15), 48 h (Day 16), 96 h (Day 18), and 144 h (Day 20) after the last dose of ASN51; and at follow-up

PET subjects will have the same timepoints as PBMC-only subjects, plus 2 additional samples at imaging session 3 at about 2 h before and 2 h after the PET scan.

Samples scheduled immediately before the PET scan should be taken as close as possible to the planned start of the PET scan. Samples scheduled for the end of the PET scan should be taken as soon as possible after the PET scan is finished. Samples scheduled during the PET scan should be taken either before or after the PET scan, as close to the scheduled timepoint as possible.

When more than one assessment is scheduled at a specific timepoint, PET procedures should be prioritised (if applicable), followed by PK, PBMC, and scheduled safety assessments. Unscheduled safety assessments due to an emergency should always be prioritised. Blood sampling should be done on time. Other procedures should be done as close as possible to the scheduled timepoint.

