16.2.9 Pharmacodynamic data analyses

O-GlcNAcylation of PBMCs will be summarised using the PD population.

Time invariance of target engagement will be investigated by comparing the PD and PK/PD relationship over time.

Food effect on the PBMC assay will be investigated by comparing Day 11 and 14 PBMC data.

In addition to the descriptive statistics of the PBMC data (ie N, mean, median, SD, min, max, CV%), time-matched PBMC parameters (Day 1 vs Day 14, and Day 11 vs Day 14) will be assessed using an Analyses of variance (ANOVA) approach.

ANOVA will be performed on the natural log(ln)-transformed PBMC parameters. Each ANOVA will include calculation of least square means (LSM), the difference between LSM of the two conditions, and the standard error and 90% confidence interval (CI) associated with this difference. The LSM, difference in LSMs, and associated 90% CI will be back transformed to present geometric LSM, the ratio of geometric means, and associated 90% CI. The 90% CI of geometric mean ratio will be calculated to check whether it lies within the interval 0.70 to 1.43.

Furthermore, PBMC PK/PD of Day 1 and Day 14 will be investigated by a regression analysis, where slope and intercept will be compared with appropriate statistical methods descriptively.

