**Template T\_ANOVA1**

Table 14.2.xx Summary of analysis of time-matched change from baseline plasma PBMC data using analysis of variance -Day 1 vs Day 14 and Day 11 vs Day 14 (% above baseline)

Treatment	RelativeTime	LS Means			Day 1 vs Day 14			Day 11 vs Day 14		
		Planned		Mean Ratio	SE	90% CI	Geometric		Mean Ratio	SE
		Day 1	Day 11				Day 1	Day 14		
Treatment 1 (N=xx)	Pre-dose	NA	xxxx	NA	NA	NA	x.xx	x.xx	x.xx	x.xx
	8 h	xxxxx	xxxx	x.xx	x.xx	(x.xx, x.xx)	x.xx	x.xx	(x.xx, x.xx)	
	12 h	xxxxx	xxxx	x.xx	x.xx	(x.xx, x.xx)	x.xx	x.xx	(x.xx, x.xx)	
Treatment 2 (N=xx)	Pre-dose	NA	xxxx	NA	NA	NA	x.xx	x.xx	x.xx	x.xx
	8 h	xxxxx	xxxx	x.xx	x.xx	(x.xx, x.xx)	x.xx	x.xx	(x.xx, x.xx)	
	12 h	xxxxx	xxxx	x.xx	x.xx	(x.xx, x.xx)	x.xx	x.xx	(x.xx, x.xx)	

Source: Listing 16.2.xx

NA = not applicable

Template T\_REGR

Table 14.2.xx Summary of ANCOVA analysis of PBMC and PK concentration to compare intercepts and slopes between Day 1 and Day 14

Treatment	Parameter	Estimate	SE	95% CI	P-Value
Treatment 1 (N=xx)	Intercept	xx.x	xx.xx	x.xxx	x.XXX
	PK Concentration	xx.x	xx.xx	x.xxx	x.XXX
	Day 1	xx.x	xx.xx	x.xxx	x.XXX
	Day 14	xx.x	xx.xx	x.xxx	x.XXX
	PK Concentration*Day 1	xx.x	xx.xx	x.xxx	x.XXX
	PK Concentration*Day 14	xx.x	xx.xx	x.xxx	x.XXX
Treatment 2 (N=xx)	Intercept	xx.x	xx.xx	x.xxx	x.XXX
	PK Concentration	xx.x	xx.xx	x.xxx	x.XXX
	Day 1	xx.x	xx.xx	x.xxx	x.XXX
	Day 14	xx.x	xx.xx	x.xxx	x.XXX
	PK Concentration*Day 1	xx.x	xx.xx	x.xxx	x.XXX
	PK Concentration*Day 14	xx.x	xx.xx	x.xxx	x.XXX

Source: Listing 16.2.xx

Programming notes: *Include timepoints: 8 h, 12h and 24 h*

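### The Day 1 versus Day 14 PBMC–concentration ANCOVA omits subject, so its 95% CIs and P-values are miscalibrated, and its straight lines can differ between days when a saturable relation has not changed

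*SAP*

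**What the plan says.** SAP section 16 plans a regression of PBMC change from baseline on plasma concentration for Days 1 and 14, "where the slopes and intercepts will be compared statistically for each treatment". The model is an ANCOVA: "Time point, PK concentration and PK concentration by time point interaction will be fitted as fixed effects". Concentration is a continuous covariate and time point is categorical. On output, "The estimates, standard errors, associated 95% CI and P-values will be reported".

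Shell `T_REGR` (SAP 19.2.1) has rows for intercept, concentration, Day 1, Day 14 and the two concentration-by-day terms, so time point here means study day. Its programming note reads "Include timepoints: 8 h, 12h and 24 h". The shell has no time-of-day column, which points to one pooled fit per dose. Neither document mentions a subject effect, random effect, covariance structure or robust standard error for this model, nor a transformation of concentration or an Emax form.

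Protocol 16.2.9 describes the same analysis as one "where slope and intercept will be compared with appropriate statistical methods descriptively".

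**The concern.** Each subject contributes several records to the fit, and all of them are scaled to that subject's own Day 1 pre-dose value (note to listing template `L_PBMC_PG`). Least squares treats the records as independent, so the standard errors are wrong. The direction differs by term: contrasts that lean on differences between subjects come out too liberal, and contrasts within subjects too conservative.

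Separately, the drug accumulates, so Day 14 samples a higher part of the concentration range than Day 1. Two straight lines fitted to two parts of one curve have different slopes and intercepts even if the curve is identical on both days. The plan reads such a difference as a change over time.

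The relation between concentration, PBMC target engagement and brain occupancy over time is a secondary PK/PD endpoint, and SAP section 16 uses the comparison to examine time invariance of target engagement. Protocol 6.4 says the trial's results will guide dose selection for patient studies. The addition of P-values to what the protocol planned as a descriptive comparison is not listed in SAP section 17.

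**Working it through.** The documents give no power, error-rate or sample-size figure for this analysis, so there is no planned number to reproduce. The check counts the records and then simulates the model as written.

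**1. Pairs per dose.** Each dose has 2 PBMC-only and 4 PET subjects. The sampling times come from Protocol 12.1, notes 19 and 20.
- On Day 1, PK samples exist at 8, 12 and 24 h. PBMC samples exist at 8, 12 and 24 h (PBMC-only) or 8 and 24 h (PET). Pairs: 2×3 + 4×2 = 14.
- On Day 14, PK is taken "before and at 0.25, 0.5, 1, 2, 4, 6, and 12 h after dosing on Day 14" and again at 24 h, so there is no 8 h PK sample. PBMC for PET subjects is taken "before and at 4 h, and 8 h after dosing on Day 14" and at 24 h, so there is no 12 h sample. Pairs: 2×2 + 4×1 = 8, six of them at 24 h.
- Total: 14 + 8 = 22 pairs from 6 subjects. The four-parameter model claims 22 − 4 = 18 residual df; with subject blocks it would be 22 − 4 − 5 = 13.

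Other counts are possible. PBMC samples alone give 2×6 + 4×4 = 28 records, and a full 8/12/24 h schedule gives 6×3×2 = 36.

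**2. Within-subject correlation.** The documents give none. Two differences from a shared baseline, with independent errors of equal variance, have correlation 0.5, so zero is implausible. The range assumed is 0.5–0.8.

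**3. Error rates with no true effect.** Settings: additive subject differences, 6 subjects, nominal 5% tests, 4,000 runs, SAP model by least squares.

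| Test | 22 pairs | 36 records |
|---|---|---|
| Day 1 slope | 12–17% | 16–26% |
| Day 14 slope | 8–12% | 16–26% |
| Slope difference (interaction) | about 5% | 8–12% |
| Day (intercept difference) | 0.2–1.7% | 0.2–1.5% |
| Intercept and slope jointly | 10–15% | 17–26% |

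With a subject block, every rate is 4.5–5.7%. A separate run with 28 records shows the same pattern: at correlation 0.5, Day 2.4%, slope difference 6.6%, Day 1 slope 12% and joint 11%. At correlation 0 all tests are at 4–5%.

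**4. Concentration ranges.** Protocol 6.7 keeps subjects on the ward "until 6 days (ie 3 half-lives) after the last study drug administration". Half-life = 6 × 24 / 3 = 48 h. With one compartment and 14 daily doses, accumulation R = (1 − 2^(−14×24/48)) / (1 − 2^(−24/48)) = 0.992 / 0.293 = 3.39. In units of the initial single-dose concentration, 8–24 h covers 0.89–0.71 on Day 1 and 3.02–2.40 on Day 14. These do not overlap within a subject.

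**5. Effect of curvature.** For an unchanged Emax relation, the local slope on Day 1 divided by that on Day 14 is ((1 + R·x)/(1 + x))², where x is Day 1 concentration/EC50. It equals 3.2, 4.8 and 6.7 at x = 0.5, 1 and 2.

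Simulated false findings follow (1,500 runs, additive subject SD 15% of Emax, EC50 0.5–2 in the units of step 4, half-life 48 h):

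| Setting | Residual SD 5% of Emax | Residual SD 15% of Emax |
|---|---|---|
| Interaction, 22 pairs | 14–24% | 9–14% |
| Joint, 22 pairs | 23–32% | 13–17% |
| Interaction, 36 records | 27–38% | 15–21% |
| Day, 22 pairs, SAP model | 7–17% | 4–10% |
| Day, 22 pairs, subject added, lines kept straight | 61–82% | 12–21% |

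With proportional 30% subject differences on 22 pairs, the interaction rate is 7–16% and the joint rate 15–30%. On 22 pairs the false interaction largely disappears at a 24 h half-life (0–4%) or at EC50 10 with a 48 h half-life (4–5%).

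**6. Check of the remedy.** Both doses were pooled with a subject block, an unchanged Emax truth and an assumed dose ratio of 2 or 4. The false Day effect is 4–8% with a common Emax curve, 1–6% with log concentration and 51–100% with a straight line.

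**The case against.** - **The between-day tests are not inflated by the missing subject term on the 22 pairs.** This stands. The slope difference is at about 5% and the Day test is conservative. The inflated rates belong to the individual slopes and to a joint test that the SAP does not name. The shell lists six rows for four estimable parameters, so which day's slope is printed depends on coding. But a Day test at 0.2–1.7% means intervals that are too wide and real drift that is under-called, so the output is still wrong.
- **File note Ward 2 changed the scheduled times and is not available here.** This stands as a limit on the pair count. The missing 8 h PK sample on Day 14 should not be treated as a defect in itself. No change of times supplies a subject term.
- **The model may be meant as one fit per time of day.** The shell does not suggest it. Each subject would still give two correlated records. A 24 h-only fit then gives 0.2–1.4% for Day and 2–3% for the interaction under the null: smaller distortion, on the conservative side.
- **Saturation is assumed.** This stands. EC50, doses and variances are not visible.
- **The stakes are low.** The trial has no null hypotheses and no decision rule here. Time invariance is also examined by the Day 1 versus Day 14 ANOVA. The protocol did allow appropriate statistical methods, though only descriptively. This limits the consequence but does not justify printing miscalibrated P-values.

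**Conclusion.** The concern holds. The omission of subject is plain in the text. Its size depends on a within-subject correlation that the documents do not give, and its direction can differ if subject differences are proportional rather than additive. For the slope difference on the 22 scheduled pairs it does little harm; for the separate slopes and the Day intercept the stated error rates are clearly off.

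The straight-line problem is conditional: it needs a half-life near 48 h and saturation within the sampled range. Where those hold, it is the main source of false drift, and adding subject alone makes the Day test worse.

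This should be corrected before the analysis is run. It does not affect the PBMC summaries or the PET results.

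**What to change.** Make both changes together in SAP section 16 and shell `T_REGR`.

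1. Add subject, as a random intercept with Kenward-Roger degrees of freedom or as a block.
2. Replace the comparison of two straight lines by one concentration–response relation across both doses: Emax, or log concentration if Emax cannot be estimated. Test time invariance as a Day shift, say which parameter shifts, and report the shift with its CI. Plot the Day 1 and Day 14 concentration ranges so that the reader can see how far they overlap. Do not read unequal straight-line slopes or intercepts as time variance.

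Also state which PK/PBMC pairs enter the model, and record the move from a descriptive comparison to P-values in SAP section 17.

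The cost is SAP wording and modest SAS programming, with no new data. There are three limits:
- Emax may have to be fixed with so few subjects.
- A subject intercept does not absorb subject-by-day variation. In the 28-record null simulation at correlation 0.5, adding a subject-by-day SD of half the total SD of the other components left the Day test at about 10% even with a subject block.
- The Day-shift test is weak. For a true shift of 15% of Emax on the scheduled pairs, power is 34–49% at residual SD 5% of Emax and 8–12% at 15%, so a non-significant shift must not be reported as proof of invariance.
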